## 9 Study discontinuation and completion

### 9.1 Discontinuation

#### 9.1.1 Discontinuation of study treatment

If discontinuation of study treatment occurs, the investigator should make a reasonable effort to understand the primary reason for the patient's premature discontinuation of study treatment and record this information. Patients who discontinue from study treatment agree to return for end of treatment follow-up visits indicated in the Assessment Schedule (refer to [Section 8](#)).

If the patient cannot or is unwilling to attend any visit(s), the site staff should maintain regular telephone contact with the patient, or with a person pre-designated by the patient. This telephone contact should preferably be done according to the study visit schedule.

Patients will be treated under hospital supervision during the treatment period. Discontinuation of study treatment for a patient occurs when study drug is permanently stopped earlier than the

protocol planned duration, and discontinuation can be initiated by either the patient or the investigator.

The investigator must discontinue study treatment for a given patient if, on balance, he/she believes that continuation would negatively impact the patient's risk of trial participation.

Study treatment must be discontinued under the following circumstances:

- Patient request
- Pregnancy
- Use of prohibited treatment as per recommendations in [Table 6-4](#)
- Any situation in which continued study participation might result in a safety risk to the patient and/or any adverse events that in the judgment of the investigator, taking into account the patient's overall status, prevent the patient from continuing participation in the study
- Unsatisfactory therapeutic effect
- Emergence of the following adverse events: severe nausea/vomiting, severe pruritus, increases in QTcF to > 500 ms (based on repeat ECGs), development of ventricular arrhythmia or clinically significant (symptomatic) bradycardia.
- Any laboratory abnormalities that in the judgement of the investigator, taking into consideration the patient's overall status, prevent the patient from continuing participation in the study (e.g., increase in liver enzymes > 3 times the upper limit of normal (see [Section 16.2](#)))
- Deviation from the planned dose regimen for the study drug (e.g., vomiting of the replacement dose within 2 hours of intake)

[figure not shown]

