2.8.2 Laboratory data

Descriptive statistics will be generated for all clinical laboratory tests performed (actual values and changes from baseline) for three groups of laboratory tests (hematology, clinical chemistry and urinalysis) by laboratory test, visit and treatment group. Maximum change from baseline during study will also be reported. Change from baseline will only be summarized for patients with both baseline and post baseline values and will be calculated as:

$$\text{change from baseline} = \text{post baseline value} - \text{baseline value}$$

The following laboratory parameters will be analyzed for hematology test group: hemoglobin, platelets, white blood cell count, Reticulocytes, Haptoglobin, hematocrit, red blood cell (RBC) count, lymphocytes, lymphocytes (%), monocytes, monocytes (%), eosinophils eosinophils (%), neutrophils, neutrophils(%) , basophils, and basophils (%) .

The following laboratory parameters will be analyzed for Biochemistry test group: creatinine, total bilirubin (TBL), direct bilirubin, alanine aminotransferase (ALT), aspartate aminotransferase (AST), alkaline phosphatase (ALP), glucose, blood urea nitrogen (BUN). Sodium, potassium, calcium, creatinine, uric acid, gamma glutamyltransferase (GGT), magnesium, chloride, and total protein, albumin, INR, Thyroid Stimulating hormone (TSH), Thyroxine Free T4.

Change from baseline will only be analyzed for Hemoglobin, RBC, platelets, TBIL, ALT, AST.

Box plots for hematology and biochemistry parameters will be provided using normalized values, by dividing a value by its upper normal limit. Normalized values are used in the box plots since lab units and normal ranges could vary according to each site and also according to a certain age group. All lab values outside the normal ranges (High/Low) will be highlighted. The lab parameters without the normal reference ranges will be excluded from this plot.

Summary with frequency and percentage of patients with liver related events as defined in [Table 2-1](#) will be provided by treatment:

Table 2-1 Liver-related events

Parameter	Criterion
ALT	>3xULN; >5xULN; >8xULN; >10xULN; > 20xULN
AST	>3xULN; >5xULN; >8xULN >10xULN; >20xULN
ALT or AST	>3xULN; >5xULN; >8xULN >10xULN; >20xULN
ALT or AST and TBL	ALT or AST > 3 × ULN and TBL > 2 × ULN ALT or AST > 5 × ULN and TBL > 2 × ULN ALT or AST > 10 × ULN and TBL > 2 × ULN
TBL	>1.5xULN, >2xULN, >3xULN
ALP	>2xULN, >3xULN
ALP & TBL	ALP >3xULN & TBL >2xULN

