2.8.3 Other safety data

2.8.3.1 ECG and cardiac imaging data

Average triplicate ECG measurements will be used for the summary.

The following quantitative variables will be summarized: heart rate, RR interval, PR interval, QRS interval, QT interval, QTcF (QT interval corrected for heart rate according to Fredericia) and QTcB (QT interval corrected for heart rate according to Bazett) for each timepoint and maximum post baseline value.

Descriptive summary statistics for the change from baseline for each post-baseline visit will be performed by ECG parameters and treatment group.

To assess the dynamics of QTc, HR and body temperature, patients with notable QT, HR and fever (≥ 37.5 °C, axillary equivalent) by timepoint will be provided. Notable criteria is provided below.

To assess the temporal correlations, mean change of QTcF over time, mean change of ECG HR over time, mean change of temperature over time, and PK concentration of KAF156 and lumefantrine over time will be plotted with all panels aligned on the x-axis (Time after dosing).

Post treatment max QTcF/QTcB increase from baseline will be calculated for each patient and 2-sided confidence intervals for the difference between the 2 treatment groups will be calculated based on two sample t-test using the 80% confidence level for the run-in cohort.

Post treatment QTcF/QTcB increase from baseline at common post-baseline timepoints (48H, Day 8, and Day 43) will be calculated for each patient and 2-sided confidence intervals for the difference between the 2 treatment groups will be calculated based on two sample t-test using the 90% confidence level for Cohorts 1 and 2.

QTc will be summarized categorically by computing the number and percentage of patients at each time point and at the maximum post baseline value with following:

- QT, QTcF, or QTcB
 - > 450 and \leq 480 ms
 - > 480 and \leq 500 ms
 - > 500 ms
 - Increase from Baseline of \geq 30 ms to < 60ms
 - Increase from Baseline of \geq 60 ms
- HR for age <18 years
 - > 90th percentile defined in [Table 2-2](#)
 - < 10th percentile defined in [Table 2-2](#)
- PR
 - Increase from baseline >25% and to a value > 200 ms
 - New value of > 200 ms
- QRS
 - Increase from baseline >25% and to a value > 120 ms
 - > 120 ms

Table 2-2 Heart rate cut-offs (beats/minute) based on centile charts

Age Range#	10 th percentile	90 th percentile
Birth	107	148
0 – <3m	123	164
3 – <6m	120	159
6 – <9m	114	152
9 – <12m	109	145
12 – <18m	103	140
18 – <24m	98	135

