Post-baseline safety	Summary visit information (e.g., lab, ECG, etc.)	The measurement closest to the target day/time will be used. In the event two measurements are taken equally apart, the first one will be used. If ECG is repeated, the higher value (worse case) of average triplicate between the scheduled and the repeated will be used for each measurement. Note, in such situations, the value used for analysis may be from the scheduled visit for some measurements but from repeated visit for other measurements.
Post-baseline safety	Notable abnormalities (e.g., lab, ECG, VS)	The most extreme measurement in the window will be used. Note this means a patient can have a notably high and notably low measurement within a window

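### SAP 2.8.3.1 counts low ECG heart rate at the maximum post-baseline value, so its across-visit row greatly undercounts children who ever had a low reading

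*SAP*

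**What the plan says.** SAP section 2.8.3.1 has one introductory sentence for all categorical ECG outputs. It asks for the "number and percentage of patients at each time point and at the maximum post baseline value with following" categories of QT/QTc, heart rate, PR and QRS. Heart rate has two limits for patients under 18 years: above the 90th percentile, and "< 10th percentile defined in" Table 2-2. The quantitative ECG variables are likewise summarised "for each timepoint and maximum post baseline value". No minimum post-baseline heart rate appears in the section.

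Table 5-7 (SAP 5.1.4) has two post-baseline safety rules that mention ECG. For visit summaries, when an ECG is repeated, "the higher value (worse case) of average triplicate between the scheduled and the repeated will be used for each measurement". For notable abnormalities, the most extreme measurement in the window is used, and the table says that a patient may then be both notably high and notably low. The SAP does not say which rule applies to the heart-rate categories.

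Protocol section 10.2.4 names bradycardia as a possible effect of many antimalarials. Protocol section 9.1.1 lists "clinically significant (symptomatic) bradycardia" among the events that lead to stopping study treatment.

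**The concern.** The maximum is the worst case for QTc, PR, QRS and high heart rate. It is the best case for low heart rate. The introductory sentence opens with QTc and seems to have been written for it, with heart rate added underneath. If the maximum was meant for QTc only, then no across-visit ECG count of low heart rate is defined at all. Either way the text needs correcting.

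At stake is the row that a reader of the study report would consult to learn how many children ever had a low ECG heart rate. As written it answers a different question: how many were low at every ECG. The answer also depends on the number of ECGs, which differs between the arms of Cohorts 1 and 2.

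**Working it through.** The plan gives no figure to reproduce. The size is illustrated with the plan's own limits and schedule.

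**One child.** Age 6 to <8 years, lower limit 74 bpm. Seven readings of 70, 66, 72, 78, 80, 85 and 88 include three below 74. The maximum is 88, so the across-visit row does not count the child.

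**Inputs from the documents**
- Table 2-2, age 6 to <8 years: 10th percentile 74, 90th percentile 111. If normal, mean = (74 + 111)/2 = 92.5 and SD = (111 − 74)/(2 × 1.2816) = 14.4.
- Post-baseline ECGs, protocol Tables 8-2 and 8-3: KAF156/LUM-SDF for 2 days, 7 (24, 27, 30, 48, 72 h, Day 8, Day 43); for 3 days, 9 (51 and 54 h added); Coartem, 4 (48, 68 h, Day 8, Day 43).

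**Assumptions not in the documents**
- Equal within-child correlation ρ of 0.3 to 0.7.
- A mean slowing of 0, 10 or 20 bpm, either sustained or gone by Day 8.
- Fever and repeat ECGs are ignored.

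**Formulas.** Given a child's random level b (standard normal), the chance that one reading is low is p(b) = Φ{[(74 − 92.5 + slowing)/14.4 − √ρ·b]/√(1 − ρ)}. With K ECGs:
- counted at the maximum = average over b of p(b)^K;
- any low reading (the count at the minimum) = 1 − average over b of (1 − p(b))^K.

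Where slowing has gone by Day 8, the last two factors use no slowing.

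| ECGs | Slowing | Counted at maximum | Any low reading |
|---|---|---|---|
| 7 | none | 0.04–1.2% | 27–41% |
| 7 | 10 bpm, sustained | 0.9–7.0% | 57–76% |
| 7 | 10 bpm, gone by Day 8 | 0.3–3.3% | 52–70% |
| 7 | 20 bpm, sustained | 8–24% | 82–95% |
| 9 | none | 0.02–1.0% | 30–47% |
| 9 | 10 bpm, sustained | 0.5–5.9% | 60–81% |
| 4 | none | 0.3–2.2% | 22–30% |
| 4 | 10 bpm, sustained | 3.2–10.5% | 49–63% |

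Higher correlation raises the first percentage and lowers the second. At ρ = 0.5 with 7 ECGs the pairs are 0.3% against 34.5% (no slowing) and 3.1% against 66.8% (10 bpm).

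**Per-timepoint count.** At a single ECG the expected proportion low is 10% with no slowing. With 10 bpm it is Φ(−8.5/14.4) = 28%, and with 20 bpm Φ(1.5/14.4) = 54%. Slowing is visible there.

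**Between arms.** For the same sustained 10 bpm slowing at ρ = 0.5, the maximum counts 6.2% with 4 ECGs, 3.1% with 7 and 2.2% with 9. Equal slowing would look about half as frequent, or less, on KAF156/LUM-SDF.

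An unrestricted minimum errs the other way: with no drug effect it gives 27–47% with 7 or 9 ECGs against 22–30% with 4. With the three common times (48 h, Day 8, Day 43) the minimum gives 19–24% in either arm with no slowing, and 45–55% with a sustained 10 bpm.

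**Repeat ECGs.** Suppose the scheduled average is 70 bpm and the repeat 80 bpm. RR is about 60,000/70 = 857 ms and 60,000/80 = 750 ms. Keeping the higher value of each measurement reports 80 bpm with 857 ms, which do not belong together. For the low category, the higher-value rule would drop the 70 and the most-extreme rule would keep it.

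**The case against.** The strongest reply is that low heart rate is shown in many other places, and this is correct.
- The same sentence requires counts at each time point. SAP 2.8.3.1 also plans a display by time point of "patients with notable QT, HR and fever", change from baseline at each visit, spaghetti plots, a listing of new or worsening abnormalities and, for the DMC, a class below 50 bpm.
- The maximum RR interval is summarised too, and the longest RR is the slowest rate.
- SAP 2.8.3.2 gives the number and percentage of patients with newly occurring notable pulse. The low limits in Table 2-3 equal those in Table 2-2 from 12 months of age upward.

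A reader might therefore infer too much from the faulty row: that the plan must report no bradycardia whatever the drug does, or that no other patient-level count exists. The documents support neither. The pulse count is not a full substitute, because on Days 2 to 4 pulse is scheduled at 24, 48 and 72 h only and misses the ECG times at 27 and 30 h (and 51 and 54 h in the 3-day regimen).

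A reading below the 10th percentile is also not bradycardia in the protocol's sense. Protocol 10.2.4 uses a rate below 50/min with a fall of more than 25%, or with symptoms. The 27–41% with no slowing is normal variation across repeated readings.

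On repeat ECGs, the most-extreme rule names ECG abnormalities and is the natural one for the heart-rate categories. What stands is that the SAP does not say so, and that visit summaries may pair HR and RR from different traces.

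A reader might extend the point to the laboratory sentence "Maximum change from baseline during study will also be reported", since change is defined as post-baseline minus baseline and harm for haemoglobin is a fall. That rests on one reading of maximum. Falls are shown by visit, in CTCAE grades by direction (SAP 5.5) and in the protocol's shift tables to the worst value (12.5.2). It is at most a clarification of direction.

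**Conclusion.** Wrong as written, minor to moderate. The across-visit row for heart rate below the 10th percentile uses the wrong end of the data and greatly undercounts children with any low ECG reading. For equal slowing it undercounts more in the arm with more ECGs. It is not near zero in every case: a sustained 20 bpm slowing would give 8 to 24%. Bradycardia is not hidden, because slowing remains visible elsewhere.

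The percentages rest on assumed normality, correlation and slowing. Fever at the early ECGs would raise heart rates and lower both columns. The direction of the error does not depend on these assumptions, because the maximum can never be below the limit unless every reading is.

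**What to change.** 1. In SAP 2.8.3.1, define the minimum post-baseline heart rate and count the below-10th-percentile category there. Keep the maximum for heart rate above the 90th percentile, QT/QTc, PR and QRS.
2. For Cohorts 1 and 2, make the between-arm comparison of the low category at 48 h, Day 8 and Day 43, the common times that the SAP already uses for QTc change. Show the minimum over all ECGs within each arm as description only, because the common times leave out the ECGs soon after dosing. In the Run-in Cohort both groups share one ECG schedule (protocol Table 8-1), so the restriction is not needed.
3. In Table 5-7, state that the most-extreme rule governs the heart-rate categories when an ECG is repeated, and take HR and RR from the same trace in visit summaries.
4. Optionally, in 2.8.2, state the direction meant by maximum change for each laboratory parameter.

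The cost is a few lines of SAP text and small programming changes. No new data are needed.

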2.8.3.2 Vital signs

The following quantitative variables will be summarized: Body height (cm) in Cohort 2, Weight (kg), Temperature (°C), Pulse (beats/min), Supine systolic blood pressure (mmHg) and Supine diastolic blood pressure (mmHg).

Analysis in vital sign measurement using descriptive summary statistics for the change from baseline for each post-baseline visit will be performed by vital sign and treatment group. Change from baseline will only be summarized for patients with both baseline and post-baseline values and will be calculated as:

$$\text{Change from baseline} = \text{post-baseline value} - \text{baseline value}$$

The number and percentage of patients with newly occurring notable vital signs will be presented. Criteria for notable vital sign abnormalities are provided in [Table 2-3](#) below.

Table 2-3 Criteria for notably abnormal vital signs

Vital sign		Criteria
Systolic blood pressure [mmHg]	High	≥ 95 th percentile of the age and height group ¹
	Low	≤ 5 th percentile of the age and height group ¹
Diastolic blood pressure [mmHg]	High	≥ 95 th percentile of the age and height group ¹
	Low	≤ 5 th percentile of the age and height group ¹

Vital sign		Criteria	
Body temperature [°C]	High	≥ 37.5°C (axillary equivalent)	
Pulse rate [bpm] ²	High	1-<6 months	> 160
		6-<12 months	>150
		12-<18 months	> 140
		18-<24 months	> 135
		2-<3 years	> 128
		3-<4 years	> 123
		4-<6 years	> 117
		6-<8 years	> 111
		8-<12 years	> 103
		12-<15 years	> 96
		≥ 15 years	> 92
	Low	1-<6 months	<120
		6-<12 months	<110
		12-<18 months	< 103
		18-<24 months	< 98
		2-<3 years	< 92
		3-<4 years	< 86
		4-<6 years	< 81
		6-<8 years	< 74
		8-<12 years	< 67
		12-<15 years	< 62
		≥ 15 years	< 58
Weight	High	increase from baseline of ≥ 2 BMI-for-age percentile categories ³	
	Low	decrease from baseline of ≥ 2 BMI-for-age percentile categories ³	

bpm=beats per minute; NHLBI= National Heart, Lung, and Blood Institute.

¹ Fourth Report on Diagnosis, Evaluation and Treatment of High Blood Pressure in Children and Adolescents. Pediatrics 2004; 114; 555 (see section 5.6 for detailed computation)

² Fleming S, Thompson M, Stevens R, et al. Normal ranges of heart rate and respiratory rate in children from birth to 18 years of age: a systematic review of observational studies. Lancet 2011; published online March 15. DOI:10.1016/S0140-6736(10)62226-X.

³ BMI-for-age percentiles categories (P3, P5, P10, P25, P50, P75, P85, P90, P95, P97) are obtained from the WHO Growth Charts, which may be accessed from GPS II growth_data (where TESTCD=BMI' and YEAR_CHG=WHO2006 and WHO2007).

[Body mass index-for-age \(BMI-for-age\) \(who.int\)](#)

2.9 Pharmacokinetic endpoints

The PK objectives are to assess PK parameters of KAF156 and lumefantrine in fasted or fed pediatric patients and to investigate the effect of food on lumefantrine PK and KAF156 PK in a Run-in Cohort of patients 12 to <18 years old.

PK parameters such as AUC_{inf}, AUC_{last}, AUC_{0-t}, C_{168h}, C_{max} and T_{max} (if feasible), will be used to evaluate these objectives, if available.

PK concentrations below the limit of quantification will be treated as zero in summary statistics and for the calculation of pharmacokinetic parameters by non-compartmental analysis. Descriptive statistics of pharmacokinetic parameters will include arithmetic and geometric means, standard deviation (SD), coefficient of variation, (CV %), median, minimum, and maximum, etc. CV% geo-mean will be calculated using this formula; $(\sqrt{\exp(\text{variance for log transformed data}) - 1}) * 100$.

In the study, rich PK data will be collected from the Run-in Cohort whereas Cohort 1 and 2 will provide sparse PK samples. A separate PK analysis will be performed for each Cohort.

Parameters will be reported for the Run-in Cohort using non-compartmental method of analysis (using Phoenix 6.4 or higher).

Two-sided 90% confidence intervals for AUC, C_{max} and T_{max} PK parameters of KAF156 and LUM-SDF will be calculated by cohort, day and treatment group using normal or log-normal approximation as applicable. Non-compartmental PK analysis for patients with sparse data will also be conducted and feasible PK parameters will be reported. Two-sided 90% confidence intervals for geometric mean ratio for KAF156 and LUM-SDF between fed vs fasted will be provided for Run-in cohort

A descriptive statistic for concentration at all nominal time points including 168 hours post dose would also be reported for all the patients.

PK parameters/ PK concentration will also be explored graphically. PK parameters/ PK concentration in Cohorts 1 and 2 will be summarized by age subgroup and body weight subgroup as per section 2.3.

PK data may be pooled for population pharmacokinetics analysis and the broad principles outlined in the Food and Drug Administration (FDA) Guidance for Industry: Population Pharmacokinetics would be followed. Additionally, PK exposure from the first few patients in each treatment group may be compared across the treatment groups and with the historical data to ensure that exposures are within the acceptable safety and efficacy.

Analyses will be performed using the PK analysis set, PK analysis set-partial food compliance, and PK analysis set-full food compliance (see Section 2.2 for the definition).

Note that in the PK analysis set-partial food compliance for the run-in cohorts, only the PK concentrations from the dosing day, where subjects are compliant to the meal criteria, will be included in the analysis.

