Data analysis	
For ACPR (Polymerase chain reaction (PCR) corrected and uncorrected ACPR at Days 15, 29 and 43), 2-sided 95% confidence intervals will be constructed using the exact (Clopper-Pearson) method for each treatment group by cohort and for Cohorts 1 and 2 pooled. If Cohort 2 does not stop early after the first 24 patients, two-sided 95% confidence interval (CI) for the difference between two treatment groups for Cohorts 1 and 2 pooled will be provided based on Mantel-Haenszel estimate of the common risk difference stratified by cohort. In case that Cohort 2 stops early, such as after the first 24 patients, two-sided 95% CI for the difference between the two treatment groups will be provided for Cohort 1 alone using the Wilson uncorrected method. For parasite clearance time (PCT) and fever clearance time (FCT), descriptive statistics (mean, standard error, median, quartiles) will be presented using the Kaplan-Meier method for each treatment group by cohort and for Cohorts 1 and 2 pooled. In case that Cohort 2 stops early, objectives for PCT and FCT will be assessed using Cohort 1 data alone. For PK parameters of KAF156 and lumefantrine, such as AUC, Cmax, etc., two-sided 90% confidence intervals will be calculated for each treatment group and for between treatment relative difference (ratio) for relevant common PK parameters by cohort and Cohorts 1 and 2 pooled using normal or log-normal approximation as applicable.

Key words	Plasmodium falciparum malaria, KAF156, LUM-SDF, children

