### **Treatment failure related parameters:**

For the following parameters, 2-sided 95% confidence intervals will be provided for each treatment group using the Clopper-Pearson method by cohort and for Cohorts 1 and 2 pooled:

- proportion of patients with ETF
- proportion of patients with LCF
- proportion of patients with LPF

In addition, following analysis will be performed. 2-sided 95% confidence intervals for the difference between KAF156 and LUM-SDF combo and Coartem® will be provided for Cohorts 1 and 2 pooled using a Mantel-Haenszel estimate of the common risk difference stratified by cohort. 2-sided 95% confidence intervals for the difference between the 2 treatment groups for each Cohort will be constructed using the Wilson uncorrected method.

The above parameters will be determined using the uncorrected parasite counts. In addition, patients whose outcome status cannot be determined due to incomplete/missing data will be excluded from analysis.

At each visit, PCR uncorrected failure will be classified into initial infection not cleared, ETF, LCF before Day 8, recrudescence, new infection, negative PCR, missing PCR, or missing assessment. The reason will be tabulated using the FAS.

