### **12.5.3 Pharmacokinetics**

Plasma concentration data will be listed by cohort, treatment group, patient, and visit/sampling time point. Descriptive summary statistics will be provided by cohort, treatment group, and visit/sampling time point, including the frequency (n, %) of concentrations below the LLOQ and reported as zero.

Summary statistics will include mean (arithmetic and geometric), SD, CV (arithmetic and geometric), median, minimum, and maximum. Concentrations below LLOQ will be treated as zero in summary statistics and for PK parameter calculations. For geometric related mean and CV, concentrations below LLOQ will be included as half of the LLOQ value.

Pharmacokinetic parameters will be listed by cohort, treatment group, and patient. Descriptive summary statistics will include mean (arithmetic and geometric), SD, and CV (arithmetic and geometric), median, minimum, and maximum. An exception to this is  $T_{max}$  where median, minimum, and maximum will be presented.

Two-sided 90% confidence intervals for AUC, Cmax and Tmax PK parameters and C168 of KAF156 and lumefantrine will be calculated by cohort and treatment group using normal or log-normal approximation as applicable. For relevant common PK parameters (related to KAF156 and lumefantrine for Run-in cohort and related to lumefantrine for Cohorts 1 and 2), two-sided 90% confidence intervals for geometric mean ratio between the 2 treatment groups will be provided by cohort.

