After about 24 patients have been randomized in Cohort 2, PK checking along with safety and efficacy will be evaluated to see if the dose level of KAF156 and/or LUM-SDF is appropriate for this age group. Since lower lumefantrine concentration at 168 hours is associated with higher recrudescence in Coartem[®] ([WWARN Lumefantrine PK/PD Study Group, 2015](#)), lumefantrine concentration at 168 hours will be the key PK parameter to be checked. Difference in lumefantrine concentration at 168 hours between the 2 treatment groups (KAF156 and LUM-SDF combination divided by Coartem[®]) will be evaluated using the geometric mean ratio and its 90% confidence interval between the 2 groups. In the KAF156A2202 Part A, the SD of log lumefantrine concentration at 168 hours was 0.63 and 0.51 for KAF156 400 mg/LUM-SDF 960 mg QDx2 group and Coartem[®], respectively. Therefore, it's assumed that the common SD for KAF156 and LUM-SDF combination and Coartem[®] in this study is 0.57 (average of 0.63 and 0.51). Assuming that there is no difference in lumefantrine concentration at 168 hours between the two treatment groups, a sample size of 10 patients per group will provide 80% power to reject the null hypothesis that the lumefantrine concentration at 168 hours is at least 50% lower in the KAF156 and LUM-SDF group than in the Coartem[®] group at 1-sided alpha of 5% (nQuery 8.4 Module MTE0-1/Two Group t-test of Non-Inferiority in Means). To adjust for potential non-evaluable lumefantrine concentration at 168 hours, the PK checking will be performed after approximately 24 patients have been randomized and reached the visit at Day 8.

Power consideration for safety (QTcF effect) in the first 24 patients in Run-in Cohort

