Mean and median max QTcF changes from baseline were similar between the POC study KAF156X2201 with KAF156 alone and KAF156A2202 Part 'A' with LUM-SDF (internal data), which indicated that lumefantrine may not contribute to additional QTcF changes when in combination with KAF156. Therefore, we hypothesized that increase in lumefantrine exposure under fed condition may not further increase QTcF. The purpose of QTcF checking for the first 24 patients in the Run-in cohort is to ensure that there is no unacceptable increase in QTcF with food intake. A QTc increase of > 20 ms for a drug compared to placebo is listed as a serious concern in ICH E14 (2005). Hence, a NI margin of 20 ms is selected for comparing the 2 treatment groups in QTcF changes for the first 24 patients in the cohort. Considering that about 15% patients may not be evaluable for QTc change, about 10 patients per treatment group will be considered for the power calculation. In CKAF156A2202 study, the SD for maximum change from baseline to any post baseline was about 20 ms in the 8 arms. Assuming a SD of 20 ms and there is no difference in QTcF change between the 2 treatment groups, there is an 80% power to show that the treatment group with fed does not increase QTcF more than 20 ms compared to the treatment group under fasting using 2-sided 80% confidence interval (i.e., the upper limit of 2-sided 80% confidence limit for the difference between two treatment groups (fed Vs fasted) in mean maximum QTcF change is less than 20 ms) (nQuery Advisor 7.0 module MTE0-1).

4 Change to protocol specified analyses

None

5 Appendix

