For PK parameters, such as AUC_{0-24h} , C_{max} , the values for individuals will be converted into \log_e scale. Mean difference and corresponding 2-sided $100 \times (1 - \alpha) \%$ confidence intervals (CI) will be calculated using PROC TTEST by assuming normality of data on log scale. The geometric mean, the lower and upper confidence limits will be calculated by exponentiating the difference, and lower and upper confidence limit that were derived using log data.

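### The SAP leaves out between-arm intervals that the protocol specifies for Cohorts 1 and 2 (final lumefantrine ratio; ETF, LCF and LPF differences), yet records no change to protocol analyses

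*SAP*

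**What the plan says.** **Lumefantrine ratio, protocol.** Section 12.5.3 covers the PK parameters common to both arms, including those "related to lumefantrine for Cohorts 1 and 2", and says that "two-sided 90% confidence intervals for geometric mean ratio between the 2 treatment groups will be provided by cohort". The data analysis entry in the protocol summary widens this to intervals "for between treatment relative difference (ratio) for relevant common PK parameters by cohort and Cohorts 1 and 2 pooled". Section 12.5.3 also lists C168 among the parameters that receive a 90% CI in each treatment group.

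**Lumefantrine ratio, SAP.** Section 2.9 makes one commitment to a ratio: "Two-sided 90% confidence intervals for geometric mean ratio for KAF156 and LUM-SDF between fed vs fasted will be provided for Run-in cohort". Its per-group intervals cover AUC, Cmax and Tmax. The 168-hour concentration receives descriptive statistics. Section 3.1.2 keeps the protocol's early check in Cohort 2, where the C168 difference between arms "will be evaluated using the geometric mean ratio and its 90% confidence interval between the 2 groups" after about 24 patients. Section 2.15 restricts interim results for Cohorts 1 and 2 to the DMC.

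**Treatment failures.** Protocol 12.5.1 requires "2-sided 95% confidence intervals for the difference between KAF156 and LUM-SDF combo and" Coartem for the proportions with ETF, LCF and LPF: Mantel-Haenszel for Cohorts 1 and 2 pooled, Wilson uncorrected within each cohort. SAP 2.7.2.3 provides exact intervals for each treatment group and no interval for the difference.

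**Declared changes.** The SAP section headed "4 Change to protocol specified analyses" contains one word, None.

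**The concern.** An analyst who programs from the SAP's own sections would not produce two sets of comparisons that the protocol specifies, and the report would state that nothing had changed.

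The lumefantrine ratio matters more. Lumefantrine is in both arms, and protocol 4.3 gives this as a reason for choosing Coartem. Protocol 4.2 says that Day 8 lumefantrine concentration correlates with PCR-corrected ACPR at Day 29, and protocol 12.8.2 makes the 168-hour concentration the key PK parameter for the Cohort 2 check. A between-arm ratio with an interval would help to interpret the non-inferiority result, whichever way it falls. If it is added only after the data are known in an open-label trial, it carries less weight than a pre-specified comparison.

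For ETF, LCF and LPF the stake is smaller: whether the arms differ in the type of failure, shown with an interval and not only as two separate rates.

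**Working it through.** **1. Text comparison**

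| Comparison in Cohorts 1 and 2 | Protocol | SAP |
|---|---|---|
| Lumefantrine ratio, final analysis | 90% CI by cohort (12.5.3), also pooled (summary) | Not in 2.9; 5.7.3 gives a general log-scale method and names no cohort or contrast |
| C168 ratio, early Cohort 2 check | 12.8.2 | Kept in 3.1.2, DMC only (2.15) |
| 90% CI for C168 within each arm | 12.5.3 | Not in the 2.9 list; descriptive only |
| ETF, LCF, LPF differences | 95% CI, pooled and by cohort (12.5.1) | Per-arm exact CIs only (2.7.2.3) |
| Declared change | n/a | None (Section 4) |

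The dash under between-treatment comparison in SAP Table 2-4 agrees with 2.7.2.3 for ETF, LCF and LPF, but it is not decisive. The table also shows a dash for recrudescence and reinfection, for which 2.7.2.5 and 2.7.2.6 specify log-rank tests. The point rests on 2.7.2.3, and on 5.7.3 confining its risk-difference methods to ACPR rates.

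**2. The plan's own figure**

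Protocol 12.8.2 and SAP 3.1.2 size the Cohort 2 check at 10 per group for 80% power. The inputs are a common SD of log C168 of (0.63 + 0.51)/2 = 0.57, a ratio margin of 0.5 (log margin ln 2 = 0.693), a true ratio of 1 and one-sided alpha of 5%.

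- Noncentrality at n = 10: 0.693 / (0.57 × √(2/10)) = 2.72, with 18 df and critical t = 1.734. Power is 83.4%.
- At n = 9 power is 79.5%.

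So 10 is the smallest group size that reaches 80%, and the plan's figure reproduces.

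**3. Precision of the C168 ratio**

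The 90% CI around a ratio of 1 is exp(± t × 0.57 × √(2/n)), where t is the 95th percentile with 2n − 2 df.

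| Data | n per arm | t | SE (log) | Half-width (log) | 90% CI |
|---|---|---|---|---|---|
| Cohort 2 check | 10 | 1.734 | 0.255 | 0.442 | 0.64-1.56 |
| Cohort 2, all | 40 | 1.665 | 0.127 | 0.212 | 0.81-1.24 |
| Cohort 1, all | 70 | 1.656 | 0.096 | 0.160 | 0.85-1.17 |
| Pooled, unstratified | 110 | 1.652 | 0.077 | 0.127 | 0.88-1.14 |

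The group sizes are half of the planned 80, 140 and 220. With 20% not evaluable (an assumption), Cohort 1 (56 per arm) gives 0.84-1.20 and Cohort 2 (32 per arm) gives 0.79-1.27. With all patients and an SD from 0.51 to 0.63, Cohort 1 runs from 0.87-1.15 to 0.84-1.19.

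**4. Precision of a failure-type difference**

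The documents give no expected ETF, LCF or LPF rates, so equal counts in both arms are assumed over a range. The Wilson uncorrected half-width around a difference of zero is √((p − l)² + (u − p)²), where l and u are the single-arm Wilson limits.

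- Cohort 1 (70 per arm): 0, 4 or 7 failures per arm give ±5.2, ±8.8 or ±10.5 percentage points.
- Cohort 2 (40 per arm): 0, 2 or 4 failures per arm give ±8.8, ±12.1 or ±14.4 points.

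**The case against.** For the ratio, the SAP is silent and does not exclude it. SAP 2.1 says that data will be analysed according to protocol Section 12, and 5.7.3 gives a method ("Mean difference and corresponding 2-sided" intervals on the log scale) that is not limited to the Run-in Cohort. The sponsor could say that the ratio is retained by reference. This does not settle the matter: 2.1 leaves the detail to the sections that follow, and 2.9 names one contrast and omits the other. For ETF, LCF and LPF the argument is weaker still, because 2.7.2.3 sets out what will be provided. The SAP's change history notes only in general terms that secondary analysis was changed because of the protocol amendment, and that amended protocol is the document that asks for these intervals.

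Three parts of the objection stand.

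- A reader might infer that the final report could say nothing about relative lumefantrine exposure. The documents do not support that. SAP 2.9 summarises the 168-hour concentration for all patients, with geometric means for PK parameters, and 2.10 plots Day 8 concentrations by cure status. An approximate ratio could be worked out from by-arm summaries.
- A reader might infer that the comparison of treatment failures is gone. It is not. ETF, LCF and LPF are the failures that make up uncorrected ACPR, and 2.7.2.1 keeps between-arm intervals for that endpoint at Days 15, 29 and 43. SAP 2.7.2.5 keeps a log-rank test for recrudescence. Only the split by failure type loses its interval.
- Few parameters are comparable besides C168. Coartem is sampled at 24, 48 and 68 hours and on Day 8, with its last dose at 60 hours; KAF156/LUM-SDF follows a different schedule. The protocol itself limits the ratio to relevant common parameters.

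**Conclusion.** The mismatch holds. Two sets of between-arm intervals specified in the protocol are not carried into the SAP sections that govern them, and the None in Section 4 is inaccurate. It would be too strong to say that the SAP keeps no Cohort 1-2 ratio, since the early C168 check survives. That check has about 10 evaluable patients per arm in the youngest cohort and an interval of about 0.64-1.56. Full-data intervals would be about 0.85-1.17 in Cohort 1 and 0.81-1.24 in Cohort 2.

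The loss is confined to formal intervals on supportive endpoints, for which SAP 2.7.2 states no hypotheses and no multiplicity adjustment. The primary non-inferiority test, its analysis set and its margin are untouched.

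The precision figures rest on an SD of 0.57 from study A2202 Part A, in patients aged 12 years and older, so its use in younger children is an assumption. They also assume log-normal concentrations, the planned group sizes and Day 8 samples in both arms. The direction does not depend on the exact SD.

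**What to change.** - **SAP 2.9 and Table 2-5:** restore the 90% CI for the lumefantrine ratio (KAF156/LUM-SDF to Coartem), by cohort and for Cohorts 1 and 2 pooled. Apply it to C168h and to any other parameter that the two sampling schedules make comparable, naming those parameters. Add C168h to the per-arm intervals.
- **SAP Table 5-6:** as printed, it shows no 168-hour PK window for Cohorts 1 and 2. Confirm or add one, since the C168 ratio depends on it.
- **SAP 2.7.2.3 and Table 2-4:** restore the 95% CIs for the ETF, LCF and LPF differences, Mantel-Haenszel pooled and Wilson uncorrected by cohort, and extend the matching methods in 5.7.3 to these endpoints.
- **SAP Section 4:** for any comparison removed on purpose, replace None with the removal and its reason.

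The cost is a few table rows from data already planned for collection, using methods that the SAP already describes. Sample size, visits and the primary analysis do not change.
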